1. Measure and compare the change in interstitial fibrosis (morphometric analysis of trichrome stained slides) at one-year post-transplant in patients converted to everolimus, low intensity tacrolimus and prednisone versus the standard of care tacrolimus, mycophenolate and prednisone regimen.

Secondary objectives:

1. Measure and compare the estimated GFR (using the 4-variable modified MDRD equation) in patients converted to everolimus, low intensity tacrolimus and prednisone versus the standard of care tacrolimus, mycophenolate and prednisone regimen, both at one year and two years post-transplant.
2. Compare the patient and graft survival rates at one-year post-transplant in each group.
3. Measure and compare the rates of immunosuppressant discontinuation and modification for each group.
4. Measure and compare the incidence of significant immunosuppressant-related adverse drug reactions for each group.
5. Compare the rates of post-transplant infections, including CMV, BK, and admissions to the hospital for infectious causes in each group.

Endpoints 6 through 10 are exploratory:

6. Measure and compare the rates and quantity of *de novo* donor specific antibody formation at one-year post-transplant in each group; this will address the important clinical question of the risk of humorally mediated alloimmune events with CNI minimization.
7. Determine the impact of gene variants for donor APOL1, donor ABCB1, recipient cytochrome P450 3A5, and donor and recipient angiotensin receptor and angiotensin converting enzyme on the primary objectives. This endpoint addresses pathways that could potentially impact outcome but are not measured by traditional risk factors and explanatory variables such as rejection and immunosuppressant concentrations.
8. Examine changes in gene expression and urinary proteomics using high throughput methods on peripheral blood, renal biopsy tissue and urine. The rationale underlying this endpoint is that these markers could yield potential biomarkers that may be used as a companion diagnostic aid in selecting patients at particularly high risk for renal progression or CNI nephrotoxicity.

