P-Glycoprotein (PGP, ABCB1, MDR1)	G2677T/A, C3435T, C1236T	
• FK and CyA Nephrotoxicity• FK Neurotoxicity in Liver Transplant Recipients• CNI Neurotoxicity in Stem Cell Transplants• CyA DGF, Renal Function, NODAT, & CMV• FK Nephrotoxicity in Pediatric Liver Transplant• Increased Risk of Acute Rejection with CyA
Apolipoprotein L1 (APOL1)	G1 and G2	
• Kidney Disease and Kidney Failure

K. Graft Interstitial Fibrosis:

Images will be examined with a Nikon E600 microscope, and a Spot Digital Firewire camera will be used to capture 24 bit RGB color images that will be stored as TIFF files. A background image of a blank area of the slide will be initially obtained and background correction will be performed in real time to adjust for subtle irregularities in the illumination of the microscope field. The images will be acquired using the 20X objective with a numerical aperture of 0.5. Images of the cortex of the biopsy from one end to the other will be obtained in a serpentine fashion starting at one end of the tissue and working toward the other. Image analysis will be performed on the stored images using an automated macro specially written for the software package NIH ImageJ. Automated analysis of the images will be performed with operator supervision. After the software is set to differentiate the positively stained from negatively stained areas on the first image, the software will sequentially open each image, do the analysis, store the data, close the image, and move on to the next image until the entire biopsy is analyzed. The operator's only function during the analysis phase is to watch the screen and stop the process if an error is detected.

L. Donor Specific Antibodies:

Serum samples will be collected and stored at the time of each renal allograft biopsy (both protocol based and for cause). DSA screening will be performed using FlowPRA beads representing HLA-A, -B, -Cw, -DR, -DQ and -DP antigens (One Lambda, Canoga Park, CA, USA). If the screening assay is positive, determination of HLA antibody specificities will be performed using FlowPRA single antigen class I and II beads (One Lambda) and analyzed according to the manufacturer's recommendations. HLA antibody specificities will be validated using LABScreen single antigen beads using a threshold mean fluorescence intensity ≥ 300 (One Lambda).

M. Gene Expression:

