Categorical data will be evaluated based on Fisher's Exact and Chi Square tests where appropriate; descriptive statistics will be used for continuous variables to describe the two patient populations and primary outcomes in each group (% change in interstitial fibrosis and eGFR from month 3 to month 12). Student's T-test or comparable non-parametric tests (such as the Wilcoxon Rank Sum test) will be used to compare the groups for these continuous variables. Patients will be analyzed based on an intent-to-treat basis, except when prohibited by lack of follow-up 12 month biopsies. Kaplan-Meier curves with the log rank test will be used to compare patient and graft survival, acute rejection free survival, and *de novo* donor specific antibody free survival. A p-value of <0.05 will be considered statistically significant. Slope change of eGFR from 3 months to 12 months post-transplant will be calculated and compared as well.

For the genomic comparisons, patients will be grouped based on the presence or absence of known single nucleotide polymorphisms and compared for primary outcomes. If significant baseline differences are noted between groups, multivariate analysis will be conducted to control for these differences. Similar analyses will be conducted for change in mRNA expression and change in urinary proteomic excretion between month 3 and month 12.

This will be an intent-to-treat analysis with all patients undergoing randomization included in the final data analysis, even if removed from study or control medication. Patients screened and consented, but not randomized will be tracked for reasons of non-randomization, but will not be followed for clinical outcomes or included in the final analysis. These patients will be

replaced to insure a total of 60 patients (30 in each group) are randomized and followed to meet study power and sample-size.

Sample size and power: A total of 60 patients, 30 *randomized* in each arm, will provide 89% power (alpha=0.05, two-sided) to detect a significant difference in the percent change in the quantity of interstitial fibrosis between groups when comparing the three month and 12-month protocol biopsies. These calculations used the following assumptions: 10% drop out rate for each group (27 patients in each group will have baseline and follow-up biopsies), with a $64\pm41\%$ change in degree of fibrosis in the control arm and a $13\pm71\%$ change in fibrosis in the investigational arm.

Evaluation schedule:

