Assessments		Pre-Txp	Day Post-transplant							Week Post-Txp		Month Post-transplant			
Time Frame			1	2	3	4	5	6	7	2	4	3	4	6	12
RANDOMIZATION												X (10-16 week window)			
History and Physical ²		X								X	X	X	X	X	X
Vital Signs		X	X	X	X	X	X	X	X	X	X	X	X	X	X
Protocol Kidney Biopsy												X			X
Donor Specific Antibody Analysis												X			X
Pregnancy testing ⁷		X	X (anytime between day 1-7)											X	X
Serologies ¹		X													
Laboratory Assessment	CBC and Chem-7 ⁴	X	X	X	X	X	X	X	X	X	X	X	X	X	X
	Total cholesterol, HDL, LDL, triglycerides ³	X										X	X		X
	Spot Urine Protein/Creatinine Ratio											X	X		X
	Tacrolimus levels ⁵			X	X	X	X	X	X	X	X	X	X	X	X
	Everolimus levels											X	X	X	X
Clinical assessment ⁶		X	X	X	X					X	X	X	X	x	X
EKG		X													
Estimated GFR		X	X	X	X	X	X	X	X	X	X	X		x	X
Genomic, RNA and proteomic analysis ⁴												X			X
Applanation tonometry using pulse wave velocity and augmentation index		One Baseline Measurement										X			X

Foot notes:

- Includes testing for CMV, Epstein-Barr, hepatitis B & C and HIV for donor and recipients (from evaluation or within one year pre-transplant if the results were negative at pre-transplant evaluation)
- Within 48 hours prior to transplant
- Fasting for at least 8 hours
- Includes genetic SNP analysis, mRNA expression, and urinary proteomic analysis
- Tacrolimus concentrations will be measured daily during the first week post-transplant once tacrolimus is initiated
- Includes assessments of blood pressure, weight changes, arterial stiffness measurement, adverse events, study drug doses, allograft rejection, infection, need for dialysis, hospitalization, re-transplant status, and other immunosuppressant medications
- Includes pregnancy test for females of child-bearing potential

Key references:

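### De novo DSA is listed for Kaplan-Meier and log-rank analysis although it is sampled almost only at two biopsies; with actual dates, or time from randomisation, the curve misstates the one-year DSA-free rate

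*Combined protocol and SAP*

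**What the plan says.** - **Analysis.** The Statistical analysis section states that "Kaplan-Meier curves with the log rank test will be used to compare patient and graft survival", and the same sentence extends the method to de novo "donor specific antibody free survival". It gives no time origin, event-date rule or censoring rule for DSA, and no method for interval-censored data.
- **Sampling.** Section L (Donor Specific Antibodies) reads: "Serum samples will be collected and stored at the time of each renal allograft biopsy (both protocol based and for cause". In the Evaluation schedule the row "Donor Specific Antibody Analysis" is marked at month 3 and month 12 only, the same two columns as the protocol biopsy. Randomisation sits in the month-3 column as "X (10-16 week window"). No window is given for month 12.
- **Objective.** Item 6 of the objectives concerns the rates and amount of de novo "donor specific antibody formation at one-year post-transplant in each group". It falls under the statement "Endpoints 6 through 10 are exploratory".
- **Alternative already in the plan.** "Categorical data will be evaluated based on Fisher's Exact and Chi Square tests where appropriate".

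**The concern.** Kaplan-Meier estimation needs event times, and censoring that carries no information about the event. Here a typical patient has one scheduled DSA test after month 3. A positive patient becomes an event on that visit date, and a negative patient is censored on his or hers. The risk set therefore empties over the same few weeks in which nearly all events are recorded. The height of the curve then depends on how visit dates happen to be ordered, as well as on how many patients developed DSA.

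Item 6 ties this endpoint to whether lower tacrolimus exposure raises antibody-mediated risk. A DSA-free rate that is badly off in either direction would mislead on that question, even in an exploratory analysis.

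A related gap is that no DSA test is scheduled before month 3. An antibody found at month 3 cannot be dated from the trial's own samples, and as a baseline finding it cannot be attributed to the randomised regimen.

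**Working it through.** **Inputs from the plan.** 30 randomised per arm, with 10% drop-out leaving 27 with both biopsies (Sample size and power); DSA at months 3 and 12 and at for-cause biopsies (section L, Evaluation schedule); randomisation at 10-16 weeks, a 42-day spread.

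**Assumptions, because the documents give no figures.** One-year DSA incidence p of 5-30%; the spread of month-12 visits; the for-cause biopsy rate; constant hazard from randomisation.

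**The plan's own figure.** The only stated power, 89%, is for fibrosis. A difference of 64 − 13 = 51, an SD of √((41² + 71²)/2) = 57.97 and 27 per arm give 88.7% by noncentral t and 89.8% by the normal approximation. It reproduces, but says nothing about DSA.

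**Closed form, untied visit dates.** Order an arm's patients by month-12 date. When k remain at risk, the patient being seen is positive with probability p. The curve is multiplied by (1 − 1/k) if positive and by 1 if negative, an expected factor of 1 − p/k. The expected end of the curve is the product of (1 − p/k) over k = 1 to 27.

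- p = 0.20: 0.443, against a true 0.80.
- p = 0.10: 0.672, against a true 0.90.

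As a check, 0.2 × (1 + 1/2 + … + 1/27) = 0.78 and exp(−0.78) = 0.46. The k = 1 factor also shows that the curve falls to zero with probability p, whenever the last patient seen is positive.

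**Reading at day 365 instead.** If dates are symmetric about day 365, about half the patients have been seen by then. The product over k = 14 to 27 is 0.867 for p = 0.20 and 0.931 for p = 0.10. Simulation with visits spread ±30 days and no for-cause biopsies gives 0.87 and 0.93. The error is now upwards.

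**Simulation of the end of the curve.** 30 per arm, 10% without a month-12 sample, 15% with a for-cause biopsy, 4,000 runs:

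| True DSA-free rate | Actual dates ±14 days | Actual dates ±30 days | All visits on day 365, time from randomisation | Tied nominal month 12 | Simple proportion among those sampled |
|---|---|---|---|---|---|
| 0.95 | 0.84 | 0.83 | 0.83 | 0.95 | 0.95 |
| 0.90 | 0.70 | 0.69 | 0.69 | 0.90 | 0.90 |
| 0.80 | 0.49 | 0.46 | 0.47 | 0.80 | 0.80 |
| 0.70 | 0.33 | 0.30 | 0.32 | 0.70 | 0.70 |

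Perfectly punctual month-12 visits do not help if time runs from randomisation, because the 10-16 week window spreads the times. With tied nominal times the end value is right, but at month 6 the curve reads 0.998 against a true 0.93 (p = 0.20).

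**Log-rank test under equal DSA rates.**

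- Similar visit timing, for-cause biopsy rates 15% in both arms: 4.3-5.5% rejections for p of 10-30%.
- Similar visit timing, for-cause rates 10% against 40%: 4.5-5.4%.
- p = 0.20, ±30-day visits, one arm's month-12 visits later on average: about 5% with no shift, 11% with 7 days, and 25-28% with 14 days.

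**The case against.** The strongest reply has four parts.

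1. **The error is conditional.** The plan does not say that actual dates will be used, and nominal visit coding gives the right month-12 value. This stands: a reader might infer that the curve must be wrong, but the documents fix no time scale, so that does not follow. Nominal coding, however, reduces the analysis to a comparison of proportions drawn as a curve whose earlier part has no meaning.
2. **The lowest figures come from the tail.** The 44-49% is the last point, where one patient remains at risk. At day 365 the error for a true 80% is about 7 points, upwards. This also stands. It shows that the answer depends on where the curve is read, and the plan does not say where.
3. **The between-arm test is sound.** A reader might infer that unequal for-cause biopsy rates would produce false positives. The calculation does not support this. Only a systematic shift in month-12 dates between arms inflated the test, and nothing in the documents says that such a shift will occur.
4. **The endpoint is exploratory, and Fisher's test is already in the plan.** Both are true. The plan nevertheless assigns DSA to Kaplan-Meier explicitly.

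It might be added that PRA informs the choice of induction, so some antibody information predates month 3. The documents do not show that it is donor-specific.

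**Conclusion.** The point holds in conditional form. DSA onset is interval-censored by design, and the plan names a method that treats visit dates as onset times without saying how dates and censoring will be set. Under actual dates or a randomisation origin, an assumed true one-year DSA-free rate of 80% appears as about 44-49% at the end of the curve; under ±30-day actual dates it reads about 87% at day 365. Under tied nominal times the month-12 value is correct and only the curve before it is wrong.

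The sizes rest on assumed incidence and visit spread; the direction and mechanism do not depend on the exact values chosen. It would go too far to call the log-rank comparison invalid, or to say that any primary or secondary result is affected. The change is worth making because the endpoint bears on a safety question and the correction is nearly free.

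**What to change.** - Remove DSA from the Kaplan-Meier list.
- Define de novo DSA as absent in the month-3 sample and detected in any later sample through month 12. A for-cause positive counts as an event.
- State that the month-3 sample is taken before any change of regimen. The schedule puts both in one column without giving their order.
- Among month-3-negative patients, compare the proportions by Fisher's exact test, with a risk difference and confidence interval.
- State how patients without a month-12 sample are handled, including those lost through death, graft loss or refusal, and add a sensitivity analysis. The plan expects about 3 of 30 per arm to lack the follow-up biopsy. An interval-censored method is an acceptable alternative.
- Report DSA already present at month 3 separately, as a baseline finding.

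The cost is a few sentences in the Statistical analysis section, with no new samples or visits. The analysis gives up onset timing, which two scheduled samples barely measure. Fisher's test is conservative here (1.7-3.7% rejections under equal rates), but for assumed DSA rates of 10% against 40% with 27 per arm its power was 63-64%, against 59-61% for log-rank, so little is lost.

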Unfortunately, current immunosuppressive therapies are not directly aimed at preventing or treating chronic graft injury mostly due to the lack of understanding of the underlying pathophysiological mechanisms. A growing body of evidence demonstrates associations of many immune and non-immune factors that either initiate or participate to some degree in this process of inexorable graft fibrosis.⁵⁻⁷ The development of fibrosis likely reflects the dynamic interplay mediating the balance between molecules that are pro-fibrotic (TGF-beta) and anti-fibrotic (BMP-7) in their primary action(s).⁶ While immune mediated factors like cellular and/or humoral (either subclinical or clinical graft injury) may be initiators of fibrogenesis, non immune mediated factors are also likely to be major pathogenic contributors in this process. Of the non-immune factors, CNI nephrotoxicity is known to be one of the strongest contributors to non-immune graft injury and fibrosis.⁸ CNI nephrotoxicity may contribute to attrition of function of the renal allograft by inducing graft fibrosis, loss of functional tissue and eventually, graft loss.⁹ The relationship between CNI concentration, dose, and intrinsic propensity of the allograft to CNI mediated injury and the ultimate burden of CNI mediated injury is complex. Naesens et al have demonstrated that vascular and interstitial lesions in allografts are most severe when early post-transplant trough concentrations of tacrolimus were low.¹⁰ The propensity of the allograft to CNI toxicity is not uniform, i.e., peripheral concentrations of drug may not relate to injurious or fibrotic events in the allograft in a dose-linear manner. The risk of acute rejection is higher when therapeutic concentrations of tacrolimus are lower in the early post transplant period. In particular, bioavailability of tacrolimus may be lower in significant subsets of populations, such as African-Americans, who are more likely to carry the expresser phenotype for CYP3A5, which leads to rapid metabolism of substrates with subsequent reduced exposure.¹¹⁻¹³ Recent studies also point to polymorphism in the ABCB1 (P-glycoprotein) gene as an important contributor to the burden of histologic injury, likely as an effect on intra-renal concentrations of tacrolimus.¹⁴⁻¹⁷ To add a further layer of complexity, certain alleles of the apolipoprotein L1 (APO-L1) gene in the donor may confer risk for progressive allograft loss independent of acute rejection, reflecting either intrinsic proclivity to progressive non-immune injury or an inability to fully compensate for or recover from ongoing injury mediated by other mechanisms.^{18,19}

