of induction will be based on the patient's immunologic risk (PRA) or risk of developing DGF. Tacrolimus doses will be adjusted to obtain target blood concentrations 5-12 ng/mL (using LCMS) for the first 3 months post-transplant. In the investigational arm, tacrolimus will be adjusted to obtain target trough concentrations of 2-5 ng/ml after 3 months post-transplant, once the patient is transitioned from mycophenolate to everolimus. The goal everolimus trough concentrations in this group will be 3-8 ng/mL (using LCMS). In the standard arm, tacrolimus doses will be adjusted to maintain a trough concentration of 5-12 ng/mL throughout the study period. Dose adjustments for immunosuppression will be allowed based on side effects or toxicities, at the clinical judgment of the primary investigator. Trough monitoring of mycophenolic acid will not be performed unless clinically warranted and dosage adjustments from such levels will be made only with consent of the study primary investigator. In the investigational arm, everolimus will be initiated at month 3 post-transplant at a dose of 1.25 mg twice daily in African-Americans and 1 mg twice daily in non-African-Americans. Doses will be adjusted to maintain trough concentrations of 3-8 ng/ml. Corticosteroids will be based on institutional protocol and will be continued in all patients at a minimum dose of 5 mg daily of prednisone or equal potent exposure if a different corticosteroid is utilized. Antimicrobial and anti-fungal prophylaxis will be administered based on institutional protocol.

Whole blood trough level monitoring of tacrolimus will be performed as follows, at a minimum of: post-operative day 3, 5, and 7, weeks 2, 3, 4, and months 2, 3, 6, 9 and 12. Everolimus whole blood trough level monitoring will be performed as follows, at a minimum of: post everolimus conversion day 4, weeks 1, 2, 3, 4 and months 3, 6, and 9. Tacrolimus and everolimus dosing may be adjusted as medically required for toxicity or rejection.

Study duration: 42 months total, with 6 months for start-up and initiation, 18 months for patient recruitment and randomization, 12 months of patient follow-up, and 6 months for data analysis and final report/manuscript preparation.

Study design: Prospective, randomized, comparative efficacy, open label study.

Study Procedures and Definitions:

A. Supplementary medications:

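### Genotype comparisons name no arm or ancestry term and adjust only after a significant baseline test, which costs precision, leaves them open to confounding by ancestry, and cannot show effect modification

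*Combined protocol and SAP*

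**What the plan says.** Two sentences of the Statistical analysis section carry the genotype analysis. In the first, "patients will be grouped based on the presence or absence of known single nucleotide polymorphisms and compared for primary outcomes". The second reads: "If significant baseline differences are noted between groups, multivariate analysis will be conducted to control for these differences". The section defines the primary outcomes as percent change in interstitial fibrosis and eGFR from month 3 to month 12. A third sentence extends similar analyses to month 3 to 12 changes in mRNA expression and urinary proteins. Nowhere are an arm term, stratification by arm, an interaction or specific covariates given.

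Objective 7 asks for the impact of named donor and recipient gene variants on the primary objectives. The primary objective is itself a between-arm comparison of fibrosis change. Objectives 6 to 10 are labelled exploratory.

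Three other statements bear on ancestry. The rationale describes African-Americans as a group "who are more likely to carry the expresser phenotype for CYP3A5". It later counts them among higher immunologic risk groups. Under Investigational and reference therapy, the everolimus starting dose is "1.25 mg twice daily in African-Americans and 1 mg twice daily in non-African-Americans".

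**The concern.** Three separate weaknesses sit in this short rule.

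- **Precision.** The sample size section expects the arms to differ by 51 points on percent change in fibrosis. A carrier versus non-carrier contrast that ignores arm treats that difference as random error.
- **Ancestry.** Randomisation balances arms, not genotype groups. If ancestry goes with both genotype and outcome, the contrast picks up ancestry. Whether that is corrected depends on a baseline p-value, although confounding depends on the size of the imbalance and its link to outcome.
- **The question.** If a variant alters how much patients gain from conversion, its effect differs by arm, and a pooled contrast averages that away.

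At stake is whether the exploratory genotype results can be interpreted. The primary comparison does not depend on them.

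**Working it through.** **Inputs from the sample size paragraph.** 60 randomised, 27 per arm (54) with paired biopsies; percent change in fibrosis 64 ± 41 in control and 13 ± 71 in the investigational arm; two-sided alpha 0.05; stated power 89%. Carrier shares are not given, so 10%, 20%, 30% and 50% are assumed (5, 11, 16 and 27 carriers of 54).

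**1. Reproducing the plan's figure.** Pooled SD = sqrt((41² + 71²)/2) = sqrt(3,361) = 57.97. With a difference of 51 and 27 per arm, power is 88.7% (t) or 89.8% (normal). The stated 89% is confirmed. No power is stated for the genotype comparisons.

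**2. Cost of omitting arm.** Between-arm variance with equal arms = 51²/4 = 650. Total = 3,361 + 650 = 4,011, so the arm share is 650/4,011 = 16.2%. For an assumed 16 carriers and 38 non-carriers, 1/16 + 1/38 = 0.0888:
- SE ignoring arm = sqrt(4,011 × 0.0888) = 18.9 points
- SE with arm removed = sqrt(3,361 × 0.0888) = 17.3 points

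The ratio is sqrt(3,361/4,011) = 0.915, an SE about 8% smaller, whatever the carrier share.

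**3. Does omitting arm bias the contrast?** No. The expected arm imbalance between genotype groups is zero. In 20,000 simulated trials with no genotype effect (16 carriers of 54), the pooled t-test rejected 5.2% of the time.

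**4. How often the significance trigger fires** (16 v 38, two-sided 0.05; all imbalances assumed):

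| True baseline difference between genotype groups | Chance of p < 0.05 |
|---|---|
| Continuous covariate, 0.5 SD | 38% |
| Ancestry share 70% v 40% | 48% (Fisher) to 55% (chi-square) |
| Ancestry share 70% v 30% | 74% (Fisher) to 80% (chi-square) |

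When it does not fire, a 70% v 40% split passes 0.3 of any ancestry difference in outcome into the genotype contrast, and 70% v 30% passes 0.4. The documents give no ancestry effect on fibrosis, so the bias in points cannot be calculated.

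**5. Effect modification.** Suppose carrying a variant adds 25.5 points in control and subtracts 25.5 under everolimus, a 51-point interaction, with 16 carriers of 54. In simulation the pooled test rejects 6.8% of the time and an interaction test 30%.

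**6. What the interaction term can deliver.** With carriers split evenly between arms, SE = sqrt((41² + 71²) × (2/carriers + 2/non-carriers)); for 16 v 38 this is sqrt(6,722 × 0.1776) = 34.6.

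| Carrier share | SE | 95% CI half-width (1.96 × SE) | Power for 51 points | Evaluable patients for 80% power |
|---|---|---|---|---|
| 10% | 54.4 | 107 | 15% | 451 |
| 20% | 39.2 | 77 | 26% | 254 |
| 30% | 34.6 | 68 | 31% | 194 |
| 50% | 31.6 | 62 | 37% | 163 |

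**The case against.** The strongest defence is that this is an exploratory analysis, that pooling is inferred because the text never mentions arm here, and that arm is randomised. All three stand. Pooling is nevertheless the natural reading, and if another analysis is intended the plan needs the sentence that says so.

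On ancestry, the dose difference is a weak argument. It is a starting dose in one arm only, and doses are then adjusted to one trough target for everyone. The case rests instead on the protocol's own links from ancestry to CYP3A5 status and to immunologic risk. It is also fair that the trigger would usually catch a very strong ancestry imbalance (74% to 80% at 70% v 30%). At 70% v 40% it is close to a coin toss.

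The interaction term cannot settle anything in 54 patients. That stands too, and limits how its result may be reported.

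A reader might infer three stronger claims that the documents do not support:
- **That the comparison is confounded by arm.** Randomisation rules this out apart from chance imbalance. For 16 v 38 that chance component has an SD of sqrt(18.9² − 17.3²), about 7.6 points, but the ordinary t-test SE of 18.9 already contains it. It is not an extra shift.
- **That confounding by ancestry is established.** It is a risk only.
- **That the plan promises to pick out patients prone to CNI nephrotoxicity by genotype.** That language belongs to objective 8 (gene expression and proteomics), and it also covers renal progression, a prognostic question that needs no interaction term.

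**Conclusion.** The point holds in a limited form. Omitting arm costs precision, not validity: about 16% of the variance is avoidable and the SE could be about 8% smaller. This uses the plan's fibrosis means and SDs with equal arms; the eGFR outcome cannot be sized from the documents. The contrast is open to confounding by ancestry, and a significance-triggered rule in about 54 patients is unreliable protection, missing an assumed 70% v 40% imbalance about half the time. As written, the comparison cannot show whether a variant changes the treatment effect, although objective 7 ties the variants to objectives that compare arms. Adding the interaction would give an estimate, not an answer: power is about 15% to 37% even for an interaction as large as the whole planned effect. Those figures assume carrier shares of 10% to 50%, an even split of carriers between arms, and SDs of 41 and 71 within genotype. The primary analysis and its 89% power are untouched.

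**What to change.** In the Statistical analysis section:

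1. Delete the condition that adjustment follows only a significant baseline difference.
2. For each named variant, model the planned fibrosis and eGFR outcomes on genotype, arm, month-3 value and recipient race, whatever the baseline p-values. For donor genes add donor race where it is recorded.
3. From the same model with an arm-by-genotype term added, report the interaction estimate with its 95% CI as hypothesis-generating only. State beside it that power for a 51-point interaction is about 15% to 37% under the assumed carrier shares.
4. Do not carry the interaction model over to month 3 to 12 changes in mRNA or urinary protein as predictors. These arise after randomisation and may be affected by treatment, so an arm-by-change term would not measure baseline effect modification.

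The cost is SAP wording. Arm and month-3 values are already collected, and recipient race is needed for everolimus dosing. No added patients, samples or visits are required. The documents do not say whether donor race is recorded, so that covariate is conditional.
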